In May 2019, the EC requested a reassessment of the benefit-risk of tofacitinib pursuant to Article 20 of Regulation (EC) No 726/2004 due to a signal for increased risks of pulmonary embolism and mortality arising in an ongoing Pfizer-sponsored Phase 3b/4 safety study (A3921133) designed to evaluate the risk of malignancy and major adverse cardiac events in RA patients aged 50 years and older who had at least one cardiovascular (CV) risk factor. In November 2019, the Committee on Human Medicinal Products (CHMP) concluded, based on a recommendation from the Pharmacovigilance Risk Assessment Committee (PRAC), that patients treated with tofacitinib are at increased risk of venous thromboembolism (VTE) events, both for deep venous thrombosis as well as pulmonary embolism, especially in patients with risk factors for VTE. The PRAC further concluded that the risk of VTE events is dose-dependent. To minimise this risk, the PRAC recommended that warnings be added to the Summary of Product Characteristics (SmPC) regarding the increased risk of VTE observed in patients taking tofacitinib, especially for patients with known risk factors for VTE. The PRAC also recommended that treatment with tofacitinib be discontinued in patients with suspected VTE and that tofacitinib 10 mg BID for maintenance treatment is not recommended in patients with UC who have known VTE risk factors unless there is no suitable alternative treatment available. Clarifications on the posology were also added, particularly for UC patients in maintenance. Specifically, some patients (i.e., patients who failed to respond to alternative treatment options for UC such as tumour necrosis factor [TNF] inhibitor treatment) who had a reduction in response to 5 mg BID maintenance treatment may benefit from an increase in maintenance dose to 10 mg BID; for these patients, the presence of known risk factors for VTE should be considered. However, tofacitinib 10 mg BID for maintenance treatment should be used for the shortest duration possible.

The PRAC also concluded that, based on the interim analyses of Study A3921133, there is a potential increased risk of mortality. This was partly driven by an increased risk of serious infections among patients 65 years and older. As such, tofacitinib should be considered

among patients 65 years and older only if no suitable alternative treatment is available. These conclusions and revisions to the SmPC were approved by the EC on 31 January 2020.

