Subsequently, in June 2021, as a result of a signal evaluation procedure (EPITT number 19382) to assess the increased incidence rate of major adverse cardiovascular events (MACE) and malignancies excluding non-melanoma skin cancer (NMSC) in patients treated with tofacitinib for RA, the European Medicines Agency (EMA) concluded that myocardial infarction (MI), lung cancer, and lymphoma were important identified risks. To minimise these risks, and the important potential risk of MACE and malignancies excluding NMSC, the EMA recommended that the SmPC be updated to include restrictions on use of tofacitinib in patients over 65 years of age, patients who are current or past smokers, patients with other CV risk factors, and patients with other malignancy risk factors (e.g., current malignancy or history of malignancy other than a successfully treated NMSC). In these patients, tofacitinib should only be used if no suitable treatment alternatives are available.

In conjunction with the initial authorisation in March 2017, to minimise important potential and identified risks associated with the use of tofacitinib and to continue to monitor important potential and identified risks, the Marketing Authorisation Holder (MAH) implemented an educational program designed to increase awareness of the risks of tofacitinib in each member state of the European Union (EU). This program consists of routine (i.e., SmPC and patient package insert) and additional risk minimisation measures (aRMMs; i.e., a prescriber brochure, checklists for treatment initiation and treatment maintenance, and a patient alert card to distribute to patients). There is also a website where healthcare professionals (HCPs) can access the aRMM materials.

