As a result of the Article 20 benefit-risk reassessment, the MAH will additionally evaluate HCPs' compliance with the new PRAC recommendations and limitations for use to minimise the risk of VTE across all approved indications (i.e., tofacitinib should be used with caution in patients with known VTE risk factors regardless of indication and dosage), with additional focus on the use of tofacitinib 10 mg BID as a maintenance treatment for patients with UC, and use and prior treatments among patients aged 65 years and older treated with tofacitinib. The MAH will also examine tofacitinib prescribing patterns over time, as well as changes in the utilisation of tofacitinib among patients with VTE risk factors and among elderly patients aged  $\geq 65$  years following the updated recommendations and limitations for use. As a result of the 2021 signal evaluation procedure, the MAH will also assess HCPs' compliance with the new EMA recommendations and limitations for use related to tofacitinib use in patients with CV risk factors and use in patients with malignancy risk factors.b The MAH will also examine tofacitinib prescribing patterns over time in the 2021 signal evaluation procedure.

This protocol describes the drug utilisation study (i.e., component 2 described above). Data from this study, together with the findings from the tofacitinib prescriber survey (A3921334), will be used to assess whether the aRMM materials are effective. This non-interventional (NI) study is designated as a Post-Authorisation Safety Study (PASS) and is conducted by the MAH as a Category 3 commitment to the EMA.

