    - The proportion of patients who discontinue to facitinib after developing  $\geq 1$  VTE risk factor while taking to facitinib; and
    - The proportion of patients who continue taking tofacitinib after developing  $\geq 1$  VTE risk factor while taking tofacitinib;
  - Use in patients aged 65 years and older, as measured by:
    - The proportion of patients 65 years and older with no alternative treatments *prior to* initiation of tofacitinib, reported overall and by approved indication;

- The proportion of patients aged 65 years, receiving tofacitinib, who have 0 prescription dispensings of tofacitinib from the time they turn 65.5 years old through to the end of the follow-up period, reported overall and by approved indication;
- The proportion of patients aged 65 years, receiving tofacitinib, who have ≥1 prescription dispensing of tofacitinib from the time they turn 65.5 years old through to the end of the follow-up period and no history of alternative treatments *prior to* that tofacitinib prescription dispensing, reported overall and by approved indication; and
- The proportion of patients aged 65 years, receiving tofacitinib, who have ≥1 prescription dispensing of tofacitinib from the time they turn 65.5 years old through to the end of the follow-up period and a history of alternative treatments *prior to* that tofacitinib prescription dispensing, reported overall and by approved indication;
- Use in patients with CV risk factors, as measured by:e
  - The proportion of patients with evidence of  $\geq 1$  CV risk factors *prior to* initiation of tofacitinib, reported overall and by approved indication;
  - The proportion of patients with evidence of ≥1 CV risk factors *prior to* initiation of tofacitinib and no prior use of an alternative therapy (i.e., biologic), reported overall and by approved indication;
  - The proportion of patients who discontinue to facitinib after developing  $\geq 1$  CV risk factor while taking to facitinib; and
  - The proportion of patients who continue taking tofacitinib after developing ≥1 CV risk factor while taking tofacitinib;
- Use in patients with malignancy risk factors, as measured by:e
  - The proportion of patients with evidence of  $\geq 1$  malignancy risk factors *prior to* initiation of tofacitinib, reported overall and by approved indication;

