Assessment of VTE risk factors while receiving tofacitinib therapy (duration of tofacitinib therapy defined in Section 9.3.3)

VTE	Outcome: VTE risk factor	Defined as $\geq 1$ ICD-10 diagnosis code for VTE while receiving tofacitinib therapy.
Surgery, major	Outcome: VTE risk factor	Defined as $\geq 1$ procedure code for a major surgery while receiving tofacitinib therapy.
MI	Outcome: VTE risk factor	Defined as $\geq$ 1 ICD-10 diagnosis code for an MI while receiving tofacitinib therapy.
Heart failure	Outcome: VTE risk factor	Defined as $\geq$ 1 ICD-10 diagnosis code for heart failure while receiving tofacitinib therapy.
Use of combined hormonal contraceptives or hormonal replacement therapy	Outcome: VTE risk factor	Defined as ≥1 prescription dispensing of a combined hormonal contraceptives and/or hormonal replacement therapy (as identified by ATC codes) while receiving tofacitinib therapy.
Inherited coagulation disorder	Outcome: VTE risk factor	Defined as ≥1 ICD-10 diagnosis code for inherited coagulation disorder while receiving tofacitinib therapy.
Malignancy (non- metastatic and metastatic; excluding non-melanoma skin cancer)	Outcome: VTE risk factor	Defined as ≥1 ICD-10 diagnosis code for malignancy (excluding non-melanoma skin cancer) while receiving tofacitinib therapy.
Diabetes	Outcome: VTE risk factor	Defined as ≥1 ICD-10 diagnosis code for diabetes while receiving tofacitinib therapy.

Variable	Role	Operational definition
Hypertension	Outcome: VTE risk factor	Defined as ≥1 ICD-10 diagnosis code for hypertension while receiving tofacitinib therapy.
Discontinuation of tofacitinib after developing ≥1 VTE risk factors while taking tofacitinib	Outcome: VTE risk factor	Defined as ≥1 VTE risk factor while receiving tofacitinib therapy (as listed and defined above) PLUS 0 prescription dispensings for tofacitinib within a specific time window after the code for the VTE risk factor.
		Note: The time window for when to look for a tofacitinib prescription dispensing will be specific to the VTE risk factor acquired while receiving tofacitinib therapy and will be operationalized during SAP development.
		Duration of tofacitinib therapy defined in Section 9.3.3.

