### 9.7.1.2.2.1. Compliance to recommendations for limitations of use

### 9.7.1.2.2.1.1. Patients with VTE risk factors

The proportion of patients with one or more risk factors for VTE, identified prior to tofacitinib initiation, will be described and tabulated overall and by individual VTE risk factor (e.g., prior VTE, recent MI). Proportions will be stratified by "RA or PsA" and "UC."

The total number of VTE risk factors identified prior to tofacitinib initiation will also be described continuously and stratified by "RA or PsA" and "UC."

The proportion of patients diagnosed with UC, one or more VTE risk factors identified prior to tofacitinib initiation, and no use of an alternative therapy (i.e., biologic) prior to tofacitinib

<sup>oo The study outcomes that contain an ADD component will *not* be assessed in Hungary or the Netherlands. The Hungarian administrative claims database is unable to estimate ADD, either directly or by proxy, due to how tofacitinib is captured in the database. In the high-budget impact medication dataset of the PHARMO Database Network (Netherlands), neither ADD nor the number of pills per prescription is captured.

<sup>pp In GKV claims, outpatient diagnoses are reported quarterly.

<sup>qq Hungary will not have a VTE Reporting Period 1. Hungary will also not have a VTE Reporting Period 2 for PsA and UC.

<sup>IT This outcome (and all sub-outcomes) will not be assessed in Sweden because the Swedish national health registers do not capture the laboratory tests of interest. In GKV claims, it may not be possible to differentiate an ALC laboratory test from an ANC laboratory test, or an ALT laboratory test from an AST laboratory test. In the PHARMO Database Network, TB screening and viral hepatitis B and C testing are not captured.

initiation whose ADD in Week 16 through Week 23, Week 24 through Week 31, Week 32 through Week 39, and Week 40 through Week 47 was >10 mg will be described and tabulated.

The proportion of patients who discontinue tofacitinib after developing one or more VTE risk factors while taking tofacitinib will be described and tabulated overall and by individual VTE risk factor (e.g., VTE, MI). Proportions will be stratified by "RA or PsA" and "UC."

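### The pooled discontinue/continue proportion after any on-treatment VTE risk factor cannot measure compliance with a discontinuation recommendation that Section 7 cites only for suspected VTE

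*Protocol*

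**What the plan says.** Section 9.3.1 places two proportions under compliance with the limitations of use in patients with VTE risk factors: patients who discontinue, and "The proportion of patients who continue taking tofacitinib after developing" one or more such factors on treatment. The secondary outcomes in the same section repeat both by VTE Reporting Period.

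Table 3 (Section 9.3.2) lists nine on-treatment factors: VTE, major surgery, MI, heart failure, hormonal contraceptive or replacement therapy, inherited coagulation disorder, malignancy, diabetes and hypertension. Most need a single code, for example "Defined as ≥1 ICD-10 diagnosis code for hypertension while receiving tofacitinib therapy". Discontinuation is a factor on therapy "PLUS 0 prescription dispensings for tofacitinib within a specific time window" after the code. Continuation is at least one dispensing in that window. The window length is factor-specific and left to the SAP.

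On what prescribers were asked to do, Section 7 says:

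- For VTE itself: "The PRAC also recommended that treatment with tofacitinib be discontinued in patients with suspected VTE".
- For VTE risk factors generally: "tofacitinib should be used with caution in patients with known VTE risk factors regardless of indication and dosage".
- For UC maintenance at 10 mg BID: the dose "is not recommended in patients with UC who have known VTE risk factors unless there is no suitable alternative treatment available".
- From the 2021 signal procedure, for groups that include patients with CV or malignancy risk factors: "In these patients, tofacitinib should only be used if no suitable treatment alternatives are available".

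Section 9.7.1.2.2.1.1 reports "The proportion of patients who discontinue tofacitinib after developing one or more VTE risk factors while taking tofacitinib" both overall and by individual factor, with VTE named as an example. It does the same for continuation, and Section 9.7.1.3.1 repeats both by VTE Reporting Period.

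**The concern.** A compliance measure should count the action that was recommended. Here one denominator mixes patients for whom the protocol cites a recommendation to discontinue (suspected VTE) with patients for whom it cites caution, a dose limit in UC or, later, a condition about alternatives. In the pooled row, a patient who continues after a hypertension code counts the same as one who continues after a VTE.

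Two features make this worse. First, Table 3 asks only for a code or dispensing while on therapy and does not require that the condition be absent at baseline. Long-standing hypertension or diabetes, or ongoing hormonal therapy, can therefore enter as a newly developed factor and swell the denominator. Second, discontinuation is defined only by the absence of a dispensing in the window, so stopping for lack of effect, intolerance or any other reason counts as a response to the factor. No reference proportion is planned that would show how much stopping to expect anyway.

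At stake is the reading of the pooled row and of its change across the VTE Reporting Periods. Both can be driven by the mix of factors and by ordinary persistence rather than by what prescribers do after a VTE.

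**Working it through.** **1. The plan's own precision figure.** Section 9.5 uses n = P(1−P)z²/e² with P = 0.50, z = 1.96 and e = 0.10: 0.25 × 3.8416 / 0.01 = 96.04, rounded up to 97. This reproduces, as do all six rows of Table 5 (385, 267, 196, 151, 119, 97). The target is thus a half-width of 10 points at about 97 patients.

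**2. The pooled row.** Let s be the share of the denominator with a VTE (with or without another factor), d the proportion of these who discontinue, and q the proportion who discontinue among the rest. Then

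pooled discontinuation = s·d + (1−s)·q.

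With perfect adherence after VTE d = 1, and with zero adherence d = 0. The difference is s, whatever q is.

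The documents give neither s nor q, so both are assumptions. With q = 20%:

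| VTE share s | Pooled, zero adherence | Pooled, perfect adherence | Difference (points) |
|---|---|---|---|
| 1% | 19.8% | 20.8% | 1 |
| 2% | 19.6% | 21.6% | 2 |
| 5% | 19.0% | 24.0% | 5 |
| 10% | 18.0% | 28.0% | 10 |
| 20% | 16.0% | 36.0% | 20 |
| 50% | 10.0% | 60.0% | 50 |

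At q = 10% or 30% the last column is the same. The VTE-specific row reads 0% against 100%.

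**3. No response instead of zero discontinuation.** If patients with VTE merely stop at the background rate b, the difference is s + (1−s)·b − b = s(1−b). With s of 1 to 5% and b of 5 to 15%, it runs from 0.01 × 0.85 = 0.9 points to 0.05 × 0.95 = 4.8 points. Under perfect adherence, pooled discontinuation would lie between 0.01 + 0.99 × 0.05 = 6% and 0.05 + 0.95 × 0.15 = 19%, so 81 to 94% would still be counted as continuing. The range for b is an assumption: under a constant hazard with 30, 40 or 50% stopping by day 365, the proportion stopping within 90 days is 8.4, 11.8 or 15.7%. The 90 days are also assumed, since the windows are left to the SAP.

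**4. Against the planned precision.** A VTE share of about 10% or less moves the pooled row by no more than the planned 10-point half-width. The denominator contains only patients with an on-treatment factor, so it will usually be smaller than the indication cohort. At P = 50% the half-width is 13.9 points for 50 patients and 21.9 for 20.

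**5. Which factors carry more than caution.** By the CV and malignancy definitions in Table 3, the 2021 restriction overlaps four of the eight other factors: MI (through coronary artery disease), diabetes, hypertension and malignancy. It dates from June 2021 and so falls within VTE Reporting Period 3 (1 October 2020 to 31 December 2023). Like the UC dose limit, it is not stated as an instruction to discontinue.

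**The case against.** The strongest reply is that the VTE-specific result is already planned, by name, overall and by reporting period. That stands. A reader might infer that adherence after VTE is lost in the pooling; the analysis sections do not support this.

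A reader might also infer that perfect and zero adherence give nearly the same pooled figure. That depends on an unstated share: it holds at 1 to 5% and fails at 20%, where the figures are 36% and 16%.

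A third tempting reading is that the other eight factors call for caution and nothing else. Section 7 does not support that, given the UC dose limit and the 2021 restriction.

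It is fair, too, that the labels for these outcomes are neutral, whereas for patients who turn 65 Table 3 explicitly separates appropriate from inappropriate continuation. The protocol therefore does not call continuation after a VTE risk factor a failure. It does, however, list it among the measures of compliance, and nothing says how the pooled row is to be read.

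Section 9.9 gives partial caveats: dispensed supply cannot be tracked after a factor appears, and caution cannot be assessed directly. Neither addresses the pooling.

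Finally, the study is descriptive and duration of therapy is tabulated. Overall duration gives some context on persistence, but not stopping over the window used for the factor.

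**Conclusion.** The point holds for the pooled row and for the compliance label on the eight rows other than VTE, and no further. The pooled discontinue and continue proportions cannot show adherence to the only discontinuation recommendation that Section 7 cites in connection with VTE. Their sensitivity to that adherence equals about the VTE share of the denominator: 1 to 5 points for an assumed share of 1 to 5%, about 20 points for 20%. The absence of a baseline-absence requirement makes a small share plausible, but the documents do not establish it. Background stopping adds to every row, the VTE row included, and its size is likewise unknown. The matter should be corrected because these proportions feed the judgement on whether the risk minimisation materials work, and the correction is cheap.

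**What to change.** Reconcile Section 9.3.1, Table 3 and Sections 9.7.1.2.2.1.1 and 9.7.1.3.1 with Section 7, without altering any clinical recommendation:

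- State that the already planned VTE-event row is the one read against the cited recommendation to discontinue.
- Label the pooled row and the other eight rows as descriptive utilisation, not compliance.
- At least for the VTE row, show the proportion with no dispensing over a window of the same length among patients on therapy without the code, at the same time since index. This is a descriptive reference and needs no comparative test.

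The cost is relabelling plus a modest amount of extra tabulation from data already extracted, multiplied by country, indication group and period if the reference is shown at that level. The main drawback is a small denominator for the VTE row: with an assumed 10 patients and P = 50%, the half-width is 31 points. In Sweden that row also carries the limitation stated in Section 9.9, that new and prior VTE cannot be reliably separated when they lie less than 12 months apart.

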  - The proportion of patients with evidence of ≥1 malignancy risk factors *prior to* initiation of tofacitinib and no prior use of an alternative therapy (i.e., biologic), reported overall and by approved indication;
  - The proportion of patients who discontinue tofacitinib after developing ≥1 malignancy risk factor while taking tofacitinib; and
  - The proportion of patients who continue taking tofacitinib after developing ≥1 malignancy risk factor while taking tofacitinib;

- Contraindicated use, as measured by:e
  - A patient *initiating* tofacitinib therapy if they have severe hepatic impairment;i
  - A woman *initiating* tofacitinib therapy if she is pregnant;
  - A patient *initiating* tofacitinib therapy if they have or have had TB in the prior 2 months;
  - A patient initiating tofacitinib therapy if they have or have had a serious and/or opportunistic infection in the prior 2 months; and
  - A woman *receiving* tofacitinib therapy during her pregnancy;
- Use with concomitant medications not compatible with tofacitinib, as measured by:
  - The proportion of patients receiving biologics and/or potent immunosuppressants *while taking* tofacitinib; and
  - The proportion of patients receiving a live vaccination *while taking* tofacitinib;j

The secondary outcomes of interest will be:

- Tofacitinib prescribing patterns over time;e,f and
- Changes in the prescribing patterns (utilisation) of tofacitinib following the updated recommendations and limitations for use implemented after the 2019 Article 20 referral and the 2021 signal evaluation procedure, specifically:
  - Use in patients with VTE risk factors, as measured by:e,f
    - The proportion of patients with evidence of ≥1 VTE risk factors *prior to* initiation of tofacitinib, reported overall and by approved indication and stratified by VTE Reporting Periodk

<sup>i The data sources are unable to reliably ascertain severity of hepatic impairment; thus, this sub-outcome may be overestimated.

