		Complete list in ANNEX 6. LIST OF ATC CODES FOR MEDICATIONS OF INTEREST TO AVOID WHILE TAKING TOFACITINIB.
Prior use of conventional synthetic DMARDs (csDMARDs)	Medication history	Defined as ≥1 prescription dispensing of a csDMARD (as identified by ATC code[s]) in the 12 months prior to the index tofacitinib dispensing.
		Complete list in ANNEX 6. LIST OF ATC CODES FOR MEDICATIONS OF INTEREST TO AVOID WHILE TAKING TOFACITINIB.
Prior use of methotrexate (MTX)	Medication history	Defined as $\geq 1$ prescription dispensing of MTX (as identified by ATC code L04AX03) in the 12 months prior to the index tofacitinib dispensing.
Prior use of anti-TB therapy	Medication history	Defined as $\geq 1$ prescription dispensing of anti-TB therapy (as identified by ATC code[s]) in the 12 months prior to the index tofacitinib dispensing.
Prior vaccination r	Medication history	Defined as $\geq 1$ procedure code and/or $\geq 1$ prescription dispensing (as identified by ATC code[s]) for a vaccination, overall and stratified by live and non-live vaccinations in the 12 months prior to the index tofacitinib dispensing.
		Complete list in ANNEX 7. LIST OF ATC CODES FOR COMEDICATIONS OF INTEREST.

Table 3.	Operational	definitions of	f study	variables in	the selected	databases

<sup>q Biologics that are dispensed or administered primarily through hospital channels may not captured (completely) in the data sources.

<sup>r This variable will not be assessed in Sweden because most vaccinations are not done in specialist care and therefore are not captured in the NPR, nor are vaccines prescribed and purchased by the patients in the pharmacies and therefore are not be captured in the PDR. Vaccination data are also unavailable in the PHARMO Database Network. In GKV claims, it is not possible to differentiate between live and non-live vaccines.

Variable	Role	Operational definition
Concomitant use of a contraindicated immunomodulator csDMARD	Comedication	Defined as ≥1 overlapping days' supply of a tofacitinib prescription dispensing and a prescription dispensing for a contraindicated immunomodulator csDMARD (as identified by ATC code[s]) during the follow-up period.

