## Table 3. Operational definitions of study variables in the selected databases

aa The data sources are unable to reliably ascertain severity of hepatic impairment and renal impairment.

bb The data sources may not be able to differentiate between active and latent TB.

<sup>z In GKV claims, outpatient diagnoses are reported quarterly.

Variable	Role	Operational definition
Compliance to recommendations for limitations of use with concomitant medications not compatible with tofacitinib		
Use of biologics approved to treat RA, PsA, or UC while taking tofacitinib cc	Outcome: Concomitant medications not compatible with tofacitinib	Defined as ≥1 overlapping days' supply of a tofacitinib prescription dispensing and a prescription dispensing for a biologic approved to treat RA, PsA, or UC (as identified by ATC code[s]) during the follow-up period.
		Note: Concomitancy with a biologic can occur even if the contraindicated medication is dispensed prior to the index tofacitinib dispensing, provided that there is $\geq 1$ overlapping days' supply with a tofacitinib prescription dispensing during the follow-up period.
		Note: This variable will be presented overall and by patients with and without $\geq 2$ tofacitinib prescription dispensings dd during the follow-up period (where the second prescription is dispensed within 15 days of the last day of the days' supply [or the equivalent] of the first prescription).
		Duration of tofacitinib therapy defined in Section 9.3.3.
		Complete list of biologics in ANNEX 6. LIST OF ATC CODES FOR MEDICATIONS OF INTEREST TO AVOID WHILE TAKING TOFACITINIB.

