### Table 3. Operational definitions of study variables in the selected databases

<sup>cc Biologics that are dispensed or administered primarily through hospital channels may not captured (completely) in the data sources.

<sup>dd Patients with  $\geq 2$  dispensings of tofacitinib are more likely to have taken tofacitinib for the full days' supply of the prescription as opposed to patients with only 1 dispensing of tofacitinib.

Variable	Role	Operational definition
Use of selected potent immunosuppressants while taking tofacitinib	Outcome: Concomitant medications not compatible with tofacitinib	Defined as ≥1 overlapping days' supply of a tofacitinib prescription dispensing and a prescription dispensing for the selected potent immunosuppressants azathioprine, 6-mercaptopurine, cyclosporine, or tacrolimus (as identified by ATC code[s]) during the follow-up period.
		Note: Concomitancy with a selected potent immunosuppressant can occur even if the contraindicated medication is dispensed prior to the index tofacitinib dispensing, provided that there is $\geq 1$ overlapping days' supply with a tofacitinib prescription dispensing during the follow-up period.
		Note: This variable will be presented overall and by patients with and without ≥2 tofacitinib prescription dispensings dd during the follow-up period (where the second prescription is dispensed within 15 days of the last day of the days' supply [or the equivalent] of the first prescription).
		Duration of tofacitinib therapy defined in Section 9.3.3.
		Complete list of selected potent immunosuppressants in ANNEX 6. LIST OF ATC CODES FOR MEDICATIONS OF INTEREST TO AVOID WHILE TAKING TOFACITINIB.

 Table 3.
 Operational definitions of study variables in the selected databases
X7	D.1.	
variable	Kole	Operational definition
Receipt of a live vaccination while taking tofacitinib ee	Outcome: Concomitant medications not compatible with tofacitinib	Defined as $\geq 1$ procedure code and/or $\geq 1$ prescription dispensing (as identified by ATC code[s]) for a live vaccination (as available) while receiving tofacitinib therapy in the follow-up period.

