#### 9.7.1.2.2.1.6. Use with concomitant medications not compatible with tofacitinib

The proportion of tofacitinib patients with concomitant use of medications not compatible with tofacitinib will be reported overall and by patients with and without  $\geq 2$  tofacitinib prescription dispensings.ss Additionally, the number of overlapping days' supply of the biologic or selected potent immunosuppressant with the tofacitinib prescription dispensing will be described continuously and categorically (e.g., 1-7 days, 8-14 days, 15-21 days, 22-30 days,  $\geq 31$  days; final cut-offs to be determined after examining the distribution of the data).

9.7.1.3. Secondary Objectives 1 and 2: Describe prescribing patterns; and Describe changes in tofacitinib prescribing patterns (utilisation) following the updated recommendations and limitations for use implemented after the 2019 Article 20 referral and the 2021 signal evaluation procedurett,uu,vv,ww

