# ANNEX 6. LIST OF ATC CODES FOR MEDICATIONS OF INTEREST TO AVOID WHILE TAKING TOFACITINIB

Class of drug	Drug	ATC code
Biologics	Abatacept	L04AA24
	Adalimumab	L04AB04
	Anakinra	L04AC03
	Certolizumab	L04AB05
	Etanercept	L04AB01
	Golimumab	L04AB06
	Infliximab	L04AB02
	Ixekizumab	L04AC13
	Rituximab	L01XC02
	Secukinumab	L04AC10
	Sarilumab	L04AC14
	Tocilizumab	L04AC07
	Ustekinumab	L04AC05
	Vedolizumab	L04AA33
Conventional synthetic DMARDS (csDMARD)	Gold preparation (sodium aurothiomalate)	M01CB01
	Gold preparation (sodium aurotiosulfate)	M01CB02
	Gold preparation (auranofin)	M01CB03
	Gold preparation (aurothioglucose)	M01CB04
	Gold preparation (aurotioprol)	M01CB05
	Hydroxychloroquine	P01BA02
	Leflunomide	L04AA13
	Olsalazine	A07EC03
	Penicillamine	M01CC01
	Sulfasalazine	A07EC01
Targeted synthetic DMARDS	Apremilast	L04AA32
	Baricitinib	L04AA37
Other DMARDS	Balsalazide	A07EC04
	Olsalazine	A07EC03
	Sulfasalazine a	A07EC01

Class of drug	Drug	ATC code
Selected potent immunosuppressant	6-Mercaptopurine	L01BB02
	Azathioprine a	L04AX01
	Cyclosporine a	L04AD01
	Tacrolimus	L04AD02

Abbreviations: ATC = Anatomical Therapeutic Chemical; cs = conventional synthetic; DMAID = diseasemodifying anti-inflammatory bowel disease drug; DMARD = disease-modifying antirheumatic drug.

a. Denotes that the medicine may also be classified as a csDMARD.

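### Annex 6 lists apremilast and baricitinib as drugs to avoid with tofacitinib, but no study variable picks them up, so their co-use would go uncounted

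*Protocol*

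**What the plan says.** One part of Primary Objective 2 is use with medications not compatible with tofacitinib. Section 9.3.1 gives it two measures: "The proportion of patients receiving biologics and/or potent immunosuppressants" while on tofacitinib, and the proportion receiving a live vaccine.

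Table 3 turns this into three rows:
- at least one day of overlapping supply of tofacitinib and "a prescription dispensing for a biologic approved to treat RA, PsA, or UC", with the biologics list taken from Annex 6;
- the same overlap rule for "the selected potent immunosuppressants azathioprine, 6-mercaptopurine, cyclosporine, or tacrolimus", also referred to Annex 6;
- receipt of a live vaccine, referred to Annex 7.

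Section 9.7.1.2.2.1.6 reports the proportion overall and by whether the patient had at least two tofacitinib dispensings. It adds that the overlapping days' "supply of the biologic or selected potent immunosuppressant with the tofacitinib prescription dispensing will be described continuously and categorically", with example bands of "1-7 days, 8-14 days, 15-21 days, 22-30 days" and 31 days or more.

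Annex 6 is headed "LIST OF ATC CODES FOR MEDICATIONS OF INTEREST TO AVOID WHILE TAKING TOFACITINIB". It groups its drugs into five classes, one of which is "Targeted synthetic DMARDS", containing apremilast (L04AA32) and baricitinib (L04AA37).

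**The concern.** The protocol's own annex describes these two drugs as ones to avoid with tofacitinib and supplies their ATC codes, yet no variable uses the codes. One day of overlapping adalimumab supply would enter the incompatible-medication outcome, while sustained overlap with baricitinib would appear nowhere in the tables. A reader of the study report who knows Annex 6 could take the absence of such cases as evidence that they did not occur, when in fact they were never looked for.

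**Working it through.** The protocol states no figure here to reproduce. The check is a cross-reading of Annex 6 against every medication row in Table 3, the outcome list in Section 9.3.1 and the analysis text in Section 9.7.1.2.2.1.6.

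**Step 1. Annex 6 by class**

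| Annex 6 class | Entries | In the incompatible-medication outcome? | Used by another Table 3 row? |
|---|---|---|---|
| Biologics | 14 | Yes | Yes: prior use, and the no-alternative-therapy variables |
| Conventional synthetic DMARDs | 10 | No | Yes: the prior-use row cites Annex 6 |
| Targeted synthetic DMARDs | 2 | No | No |
| Other DMARDs | 3 | No | In part: two entries repeat codes from the conventional synthetic class |
| Selected potent immunosuppressants | 4 | Yes | Not needed |

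So 14 + 4 = 18 Annex 6 codes feed the outcome. The targeted synthetic class is the only one with none of its codes in any row.

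**Step 2. Search of the remaining rows.** The prior-medication rows cover corticosteroids, statins, biologics, conventional synthetic DMARDs, methotrexate, anti-TB therapy and vaccines. The comedication rows cover methotrexate, corticosteroids, anti-TB therapy and "Concomitant use of a contraindicated immunomodulator csDMARD". The dispensing-based risk-factor rows cover hormonal products, antihypertensives, lipid-lowering drugs and nicotine replacement. None of these includes a targeted synthetic DMARD.

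**Step 3. Could the existing wording absorb the two drugs?** Annex 6 places them outside both its biologics class and its immunosuppressant class. The immunosuppressant row is a closed list of four named drugs. Section 9.3.2 leaves refinement of algorithms and code lists to the SAP, but refining the codes within a named class does not add a class that the outcome wording leaves out.

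**Step 4. Size.** The protocol gives no frequency of co-dispensing of tofacitinib with apremilast or baricitinib, so the number of patients affected cannot be calculated.

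**The case against.** The strongest reply is that Annex 6 is the wrong yardstick. The research question in Section 8 is compliance with the risk-minimisation materials, not with an annex. Those materials are not part of this protocol version, and the amendment log says they may change during the study. Annex 6 is also a shared code list: it serves the prior-biologic, prior-csDMARD and no-alternative-therapy variables, and the two overlap rows each point to a named subset of it. Its conventional synthetic DMARDs also lie outside the outcome, and Section 7 describes PsA trials of tofacitinib combined with a non-biologic DMARD. Outcome and annex were therefore not built to match line by line.

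Most of this stands. Being listed in Annex 6 does not by itself make a drug part of the outcome, and a reader should not infer that the study is shown to understate non-adherence. That would require knowing that the materials tell prescribers to avoid these two drugs.

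A second tempting inference is that every other non-biologic class is tracked during treatment and this one alone is missed. The documents do not support that either. The on-treatment csDMARD row is limited to contraindicated agents and cites no annex, so it cannot be said to cover all the listed csDMARDs.

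A third reply is that the SAP may modify the protocol's plans (Section 9.7). It may, and that lowers the stakes. But nothing in the protocol directs it to add this class.

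What the replies leave untouched is that a whole class in a list titled as drugs to avoid serves no variable of any kind, with no reason given.

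**Conclusion.** The point holds as a gap in the protocol's own text. The incompatible-medication outcome is fixed to biologics, four named immunosuppressants and live vaccines. Apremilast and baricitinib, which Annex 6 lists as drugs to avoid, enter no variable, so their use alongside tofacitinib would go uncounted. The textual finding is firm because it rests only on Annex 6, Table 3 and Sections 9.3.1 and 9.7.1.2.2.1.6. Its importance is less certain: the number of patients is unknown and may be small, and the status of these drugs in the risk-minimisation materials cannot be checked. This is a cheap improvement worth considering. It is not an error that undermines the outcome as defined.

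**What to change.** Add one row, *Use of targeted synthetic DMARDs (apremilast, baricitinib) while taking tofacitinib*, to Section 9.3.1, Table 3 and Section 9.7.1.2.2.1.6. Give it the rules already used for biologics:
- at least one overlapping day's supply during follow-up;
- the split by patients with and without at least two tofacitinib dispensings;
- the same overlap-day categories, so that short overlaps from switching can be told from sustained co-use.

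Report it separately. Merging it into the existing proportion would change what that proportion means. If the class is left out on purpose, a sentence in Annex 6 saying so would remove the inconsistency.

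The cost is low. The ATC codes are already listed, and Section 9.4 describes ATC-coded dispensing data in all four countries, although it does not say how completely these two drugs are captured in each. The downsides are slightly more tabulation, some counted overlap that reflects switching (as already happens with biologics), and a possible protocol amendment, since Section 9.7 requires one for major changes to primary endpoint definitions.
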